2. Specific age range of participants (e.g., 7-12 years old, 60+, etc.):

between ages of 18 and 80 inclusive

3. Indicate any vulnerable participant groups (other than children) included:

None

If "Other", please specify:

If "None" and no children are involved, answer the following question.

Has the participant selection process overprotected potential subjects who are considered vulnerable so that they are denied opportunities to participate in research?

Yes No

4. Number of participants to be included and/or enrolled in this entire study, across all study locations: 140

At Utah prior to October 2019: 20

5. Characteristics of Participants/Inclusion Criteria:

For inclusion, subjects must meet the International Headache Society criteria for chronic migraine (International Classification of Headache Disorders, 3rd edition (Headache Classification Committee of the International Headache Society, 2013; Figure 1A) - OR - subjects must meet the International Headache Society criteria for episodic migraine (Headache Classification Committee of the International Headache Society, 2013; Figure 1B) AND have at least 8 headache days per month ("high-frequency episodic migraine"). All subjects must be between the ages of 18 and 80 years-old.

To be included in the study, in the best judgment of the investigator, subjects must be stable on their current migraine treatment regimen. Stability is defined as no major changes in therapy contemplated within the next 4 months.

Subjects should be on a stable course of all prescription medications for the 4 weeks preceding enrollment.

6. Participant Exclusion Criteria:

Subjects with other light sensitive conditions, such as iritis and blepharospasm, will be excluded. Subjects with best-corrected visual acuity less than 20/40 will be excluded. Subjects with diseases of the retina, such as diabetic retinopathy and macular degeneration will be excluded. Subjects using medications known to affect the eye will be excluded (e.g. chloroquine, hydroxychloroquine, ethambutol, amiodarone). Due to constraints on the manufacture and mounting of study lenses into study frames, the study must exclude subjects who are very nearsighted (more than 4 diopters), subjects who are very farsighted (more than 2 diopters), and subjects who have more than 2.5 diopters of astigmatism.

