Because of the cyclical effects of botulinum toxin injections and other nerve blocks, patients undergoing these treatments will be excluded. Subjects must not have had any injections or blocks within 4 months of enrollment and should not receive any further blocks until they exit the study.

Subjects with *continuous daily* headache (a headache frequency of 100%) will be excluded. Subjects who do not have a headache frequency of at least 8 days per month will be excluded.

Subjects with medication overuse headache will be excluded (Figure 1C). A patient with a history of medication overuse who has not overused abortive medications for the past 4 months can be included.

Subjects who abuse alcohol or use illicit drugs will be excluded.

Subjects may continue to use their customary preventative, abortive or rescue medications for migraine throughout the trial.

7. Is a substantial percentage of the participant population anticipated to be non-English speaking?

Yes No

IRB_00086498

Created: 9/19/2015 4:57 PM

PI: [name]

Submitted: 3/29/2016

Title: Spectacle Tints and Thin-Films to Reduce Headache Frequency
in Patients with Migraine

4. Study Information

1. Design of Study (select all that apply):

Prospective Clinical Research
Randomized
Other

If Other, describe:

Active control

2. Does your study involve the use of any placebo?

Yes No

3. Length of entire study, from initiation through closeout:

30 months

4. How will participants be recruited or identified for inclusion in the study?

a. Select all methods that will be used:

In-person contact (e.g., patients, students, etc.)

Referrals

Written advertising (flyers, brochures, website postings, newspaper ads, etc.)

From a database or participant pool for which participants have given prior permission to be contacted for research studies

Other

A website has been created for recruitment purposes. This website has been optimized such that internet search engines looking for information about migraine or light sensitivity will be able to identify the site. www.migraineglassesstudy.com.

A 45-second recruitment video has been developed to aid recruitment and is embedded in the website.

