Subjects will be randomized with equal allocation to receive either tinted or thin-film coated spectacles. A random permuted block randomization will be employed. However, before receiving their study spectacles, subjects will complete a four-week "baseline period" during which no study lenses will be worn. This period will help establish the base-line characteristics of their headaches. Subjects will keep daily diaries throughout the 16-week study detailing the frequency and severity of their headaches (Figure 5).

Visit 2 (Week 4)

When subjects return after the 4-week baseline period, the research team will review their diaries. Subjects must provide at least 20 days of diary data and must have had at least 15 headache days (defined as a calendar day consisting of at least 4 hours of continuous headache). This requirement helps insure subjects meet the definition of chronic migraine. Subjects must have had at least 4 distinct headache episodes each lasting at least 4 hours during the 4-week baseline period. This requirement helps insure that subjects with continuous headache are not included in the study, as these subjects are often unresponsive to any headache treatments. Subjects whose diaries do not meet these criteria will exit the study. Subjects whose diaries indicate that they are overusing abortive pain medications will exit the study. Subjects who exit the study at this point will be given a \$25 gift card. At the discretion of the site PI or coordinator, this visit may be completed via phone. Study instruments including the diaries and questionnaires may be completed by phone or transmitted by U.S. mail, email or fax. Alternatively, these instruments may also be completed by the participant within REDCap.

Subjects whose diaries meet these criteria will complete a questionnaire and receive their study spectacles. The research team will insure the glasses fit comfortably and will instruct the subjects to wear them full time. Subjects will receive new diaries.

Visit 3 (Week 8)

The research team will review the subject's diaries, insure the subject's glasses still fit comfortably, and will instruct the subject to continue to wear the glasses full-time. Subjects will complete a questionnaire and receive new diaries. At the discretion of the site PI or coordinator, this visit may be completed via phone. Study instruments

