Serious adverse events that are deemed by the Site Investigator not to be related to the Trial will be reported to the Sponsor on a quarterly basis, by written report from the CRO.

Adverse events that are not serious will be reported to the Sponsor on a quarterly basis, by written report from the CRO.

3. Describe the types of reports that will be produced by the monitoring entity (e.g., safety, study progress, interim analysis, etc.):

Safety reports will be produced each quarter. There will be no study progress reports or interim analyses.

4. Describe the specific triggers or stopping rules for the study:

a. Under what conditions will a participant be withdrawn from the study?

A subject can always voluntarily withdraw.

At the 4-week visit, a member of the research team will review the diary entries for the past 4 weeks. Subjects who have a headache frequency less than 50% will be withdrawn. Subjects who have a headache frequency of 100% will be withdrawn.

The site investigators or principal investigator may withdraw a participant for the following reasons:

- 1) Failure to attend scheduled follow-up appointments
- 2) Failure to complete diaries or other study instruments
- 3) Failure to comply with study guidelines

b. Under what conditions will the study be modified or stopped?

There are no plans to modify the study. A similar previous study was completed at the University (IRB #47263) and no adverse events occurred.

There are no plans to stop the study. As it is minimal risk, conditions for stopping the study have not been established.

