In our previous study, a majority of subjects had statistically significant reductions in the headaches. If successful, these spectacle coatings may be the first FDA-approved treatment for migraine that specifically addresses light sensitivity. Based on our previous study, it is expected that most subjects in both arms of the study will experience at least some reduction in their light sensitivity. Results from this study will help other migraine patients determine if spectacle tints and/or thin-films might be beneficial to them.

3. Are there any costs to the participants from participation in research?

Yes No

If yes, specify:

4. Is there any compensation to the participants?

Yes No

a. If yes, answer the following:

Specify overall amount:

Subjects who complete the entire study will choose to either keep their study glasses or receive a check for \$100.

Subjects who complete the first 4 weeks of the study, but who are withdrawn because they no longer meet inclusion/exclusion criteria at the 4-week visit will receive a check for \$25.

b. Specify when participants will be paid (e.g. at each visit, at end of study, etc.):

As above.

c. If applicable, please specify payment by visit or other time interval (e.g. \$10 per visit, etc.):

Not applicable

d. If applicable, explain plan for prorating payments if participant does not complete the study:

Payments will not be prorated except as stipulated, above.

IRB_00086498

Created: 9/19/2015 4:57 PM

PI: [name]

Submitted: 3/29/2016

Title: Spectacle Tints and Thin-Films to Reduce Headache Frequency
in Patients with Migraine

7. HIPAA and the Covered Entity

1. **Does this study involve Protected Health Information (PHI) or de-identified health information?**

Yes No

a. **Select the method(s) of authorization that will be used:**

(Consent and) Authorization Document

Waiver or Alteration of Authorization

b. **Will PHI be disclosed outside the Covered Entity?**

Yes No

To whom?

FDA

And for what purposes?

The FDA may request an audit of the data if they are used to request a labeling indication as a treatment for migraine.

Does this study involve any of the following:

2. **The investigational use of a drug?**

Yes No

3. **The investigational use of a medical device?**

Yes No

4. **Is this an investigator-initiated drug or device trial lead by the Principal Investigator?**

Yes No

5. **Exposure to radioisotopes or ionizing radiation?**

Yes No

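### Entry criteria admit episodic migraine from 8 headache days a month, but a Week 4 rule applied after randomization requires 15 and would remove most of those subjects

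*Combined protocol and SAP*

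**What the plan says.** **Entry.** Item 5 of the participant section (Inclusion Criteria) opens two routes: chronic migraine, or episodic migraine in subjects who "have at least 8 headache days per month". Item 6 (Exclusion Criteria) repeats that limit: "Subjects who do not have a headache frequency of at least 8 days per month will be excluded".

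**Randomization.** Table 1 (section 4, item 6) lists randomization at Visit 1, Week 0. The Baseline Visit 1 text agrees: after allocation, and "before receiving their study spectacles, subjects will complete a four-week" baseline period without study lenses.

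**Week 4 rule.** Under Visit 2 (Week 4): "Subjects must provide at least 20 days of diary data and must have had at least 15 headache days". A headache day is defined there as a calendar day with at least 4 hours of continuous headache. The reason given is: "This requirement helps insure subjects meet the definition of chronic migraine". Subjects whose diaries fail exit the study.

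**Second Week 4 rule.** The Safety Monitoring Plan, item 4a, says: "Subjects who have a headache frequency less than 50% will be withdrawn". It gives no denominator. It also withdraws subjects at 100%.

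**Description of the exits.** Section 6 (Risks and Benefits), item 4a, describes these subjects as "withdrawn because they no longer meet inclusion/exclusion criteria at the 4-week visit".

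**Sample size.** Item 4 of the participant section reads: "Number of participants to be included and/or enrolled in this entire study, across all study locations: 140". Sample Size and Power (section 4, item 9) counts 140 as randomized, 70 per arm, after a 10% allowance for loss to follow-up. Its planning figures come from 22 pilot subjects with at least 50% and under 100% headache days.

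**The concern.** The episodic route is deliberate: it has its own label in the inclusion criteria, and its 8-day limit recurs as an exclusion. Yet the Week 4 rule applies to everyone and is justified as a check for chronic migraine. A subject with 8 to 14 headache days still satisfies the written frequency criterion, so the compensation text is wrong to describe such a subject as no longer eligible.

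A run-in normally confirms eligibility before allocation. Here it follows allocation, so every exit is a randomized subject lost. Two things are at stake:

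- **Target population.** The text does not settle whether the trial studies chronic migraine alone or chronic plus high-frequency episodic migraine. The planning inputs fit the population left after Week 4. They would not fit if episodic subjects are meant to stay.
- **Sample size.** Read literally, the 140 is counted before the Week 4 exits, and the only allowance is 10% for loss to follow-up. The text available does not say whether exits are replaced.

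The exits rest on diaries kept before any lenses are worn, so the treatment itself cannot cause them. The harm is lost sample size and an unclear population, not treatment-related selection bias.

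**Working it through.** **1. The plan's own sample size.** Inputs from Sample Size and Power: SD 18.6, correlation 0.55, difference 7.8 points, two-sided alpha 0.05, 80% power, 10% loss.

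- ANCOVA residual SD = 18.6 × √(1 − 0.55²) = 15.53.
- n per arm = 2 × (1.96 + 0.842)² × 15.53² / 7.8² ≈ 62.3, rounded up to 63.
- 63 / 0.9 = 70 per arm, or 140 in total. The plan's figure reproduces. Power with 63 per arm is 79.8% (noncentral t).

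**2. Who passes the 15-day rule.** Assume a full 28-day diary, independent days and a true average of d headache days. The pass probability is P(X ≥ 15), with X binomial (28, d/28), or d/30 if a month is taken as 30 days.

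| d | d per 28 days | d per 30 days |
|---|---|---|
| 8 | 0.5% | 0.2% |
| 10 | 4% | 2% |
| 12 | 17% | 10% |
| 14 | 43% | 29% |

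With d spread evenly over 8 to 14, the average pass rate is 15% (28-day month) or 9% (30-day month), so 85% to 91% are removed. Letting days cluster within subjects (beta-binomial, intraclass correlation 0.05 to 0.20) raises the average pass rate to 17% to 31%, so 69% to 83% are removed. With only 20 diary days recorded, the pass rate is at most about 2% under independence.

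**3. The two Week 4 floors.** For every diary length from 20 to 28 days, a count of 15 or more is at least 50%, so the Visit 2 rule removes everyone the 50% floor removes. The reverse does not hold. If frequency is taken over recorded days (an assumption), these counts meet the 50% floor but fail the 15-day rule:

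| Diary days | Headache days |
|---|---|
| 20 | 10–14 |
| 22 | 11–14 |
| 24 | 12–14 |
| 26 | 13–14 |
| 28 | 14 |

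A site applying both rules gets the Visit 2 result plus the 100% cap. Sites reading different sections would keep different subjects.

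**4. Effect on power.** The exit share e is not documented, so a range is shown. Assume exits are not replaced and come on top of the 10% loss, with SD and correlation as in the plan.

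- Analysed = 140 × 0.9 × (1 − e).
- Randomized needed to keep 126 analysed = 126 / (0.9 × (1 − e)).

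| e | Analysed | Power at 7.8 points | Difference detectable at 80% power | Randomized needed |
|---|---|---|---|---|
| 0% | 126 | 80% | 7.8 | 140 |
| 10% | 113 | 75% | 8.25 | 156 |
| 20% | 101 | 70% | 8.8 | 175 |
| 30% | 88 | 64% | 9.4 | 200 |
| 40% | 76 | 58% | 10.15 | 234 |
| 50% | 63 | 50% | 11.15 | 280 |

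**The case against.** The strongest reply is that the power loss does not follow from the contradiction alone. Once it is resolved either way, the episodic exits go: those subjects are either kept or never randomized. The 140 can also be read as counted after Week 4. Its planning inputs match subjects who pass the diary check, the primary analysis calls the 12 weeks after baseline the follow-up period, and item 4 speaks of included and/or enrolled. On that reading the calculation is coherent and needs only a clarifying sentence. This stands in part: the power table is conditional, and its 40% and 50% rows have no anchor in the documents. But the sample-size text says randomized, and Table 1 puts randomization at Week 0, so the literal reading is the one with the shortfall.

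It can also be said that most is an inference. The text gives no upper limit for episodic migraine, its defining figure is not shown, and the 8-to-14 range rests on the plan's own use of 15 days to mark chronic migraine. That is fair, and the exact probabilities depend on the model. The direction does not: every assumed rate in that range gives a pass probability below one half.

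The 50% floor and the compensation wording are lesser points, since the Visit 2 rule is the stricter floor. Finally, the text available describes masking only for subjects. Pre-treatment diaries rule out exits caused by the lenses, but not every influence on the staff who review those diaries. None of this removes the conflict between the entry criteria and the Week 4 rule.

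**Conclusion.** The point holds and must be corrected. The entry criteria and the Week 4 rule contradict each other, and following both means randomizing a named group and then removing most of it: about 69% to 91% of subjects averaging 8 to 14 headache days a month, across the models tried. The arithmetic behind 140 is sound for a population with 50% to under 100% headache days. What is unsettled is whether that is the population intended and at which point the 140 is counted.

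The cost in power depends on an undocumented exit share, on exits not being replaced, and on their adding to the 10% loss. Under those assumptions, each further 10% of exits costs roughly 4 to 8 percentage points of power.

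**What to change.** 1. Reconcile the inclusion criteria, the exclusion criteria, the Visit 2 rule, Safety Monitoring Plan item 4a and the compensation wording to one frequency criterion. State its denominator and use one headache-day definition throughout. At present the 4-hour definition appears only at Visit 2. The text of the entry criteria gives none, and the figure they cite is not shown.
2. The sponsor chooses the population. If episodic subjects are kept, restate the planning mean, SD and correlation for that population. If not, delete the episodic route from the entry criteria.
3. In either case, state in Sample Size and Power whether the 140 is counted before or after Week 4 exits and whether exits are replaced. If it is counted before and they are not replaced, restate the power.

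The cost is amendment wording in five places and one or two sentences on sample size. Keeping episodic subjects also needs new planning inputs; removing the route narrows recruitment. If the 140 is meant to be those remaining after Week 4, the number randomized rises with the exit share: 140 / 0.8 = 175 at 20%, or 140 / 0.7 = 200 at 30%.

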Subjects who do not wear glasses will be given study spectacles without any optical correction. Subjects who already wear glasses will be given customized spectacles that incorporate their optical correction. Subjects who customarily wear contact lenses will be asked to wear glasses without an optical correction over their contact lenses.

The optical properties of the thin film coating and the gray tint are shown in Figure 2. All spectacles will have the same overall optical density across the visible spectrum. This statement means that all study eyewear will appear to have the same amount of “darkness” to the subject. The total study duration will be 16 weeks

Table 1. Protocol Visit Schedule

Visit	Week	Activities
1	0	Determine eligibility
		Informed Consent
		HIT-6
		Baseline photophobia and ADL questionnaire
		Receive diary
		Randomization
2	4	Diary check
		HIT-6
		Receive glasses/Check glasses fit
3	8	Diary check
		HIT-6
		Check glasses fit

4	12	Diary check
		HIT-6
		Check glasses fit
5	16	Diary check
		HIT-6
		Final photophobia, ADL and masking questionnaires
		Keep glasses OR receive compensation and return glasses

Baseline Visit 1 (Week 0)

Subjects who meet study inclusion and exclusion criteria will be invited to participate in the study. Potential subjects will have all of their questions about the study answered. Subjects who agree to participate will sign an informed consent document and be given a copy of the document. They will fill out a baseline questionnaire regarding light sensitivity and activities of daily living (Figure 3). They will complete the 6-item Headache Impact Test (HIT-6; Figure 4) The HIT-6 is copyrighted, but its use is not restricted by the holder of the copyright and it's not necessary to get permission or pay the copyright holder for use of the questionnaire. At the discretion of the site PI or coordinator, this visit may be completed by phone. Study materials including the informed consent document and questionnaires may be transmitted by U.S. mail, email, or fax.

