9. Provide a summary of the statistical methods, data analysis, or data interpretation planned for this study. Factors for determining the proposed sample size (e.g., power) should be stated.

Preliminary Analyses

Baseline characteristics will be summarized by randomized treatment group with standardized differences between treatment groups used to assess the balance of patient characteristics between the two groups. Univariate summaries will also be performed at baseline and follow-up for the primary and secondary outcome variables. If quantitative outcome variables exhibit substantial skewness, transformations may be sought to better approximate normality.

Primary Analysis of Headache Days

The primary analysis of the efficacy of the thin-film intervention will be conducted as an analysis of covariance comparing the proportion of days during the 12 week follow-up period recorded as headache days between the thin-film treatment group and the tinted glasses group, using the proportion of headache days during the 4-week baseline as a covariate. The null hypothesis of no treatment effect on headache frequency will be rejected if the 2-sided p-value corresponding to the treatment effect is smaller than 0.05.

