In a secondary analysis, generalized estimating equations (GEE) will be applied to a generalized linear model in which the probability of reporting a headache day during the treatment period is related to a) the baseline frequency of headache days, b) the randomized treatment group, c) week of follow-up, defined as a categorical variable, and d) the interaction of the randomized treatment group with follow-up week. This analysis will be used to characterize the treatment effect over different portions of the follow-up period. A binary outcome model with a logistic link function will be used. A compound symmetry working covariance matrix will be applied and robust standard errors will be used for statistical inferences. The analysis will provide estimates of the odds ratio (with associated 95% confidence intervals and p-values) for reporting a headache day between the two treatment groups obtained separately for each follow-up month. If the interaction between the randomized treatment group and week of follow-up is not statistically significant at the $\alpha=0.05$ level, an overall estimate of the odds ratio for reporting a day with severe headache between the two treatment groups will be provided under a reduced model which excludes the randomized treatment group by follow-up week interaction. For reporting purposes, we will

also provide ratios of the probabilities for reporting headache days using a marginal means approach, with bootstrap resampling used to estimate 95% confidence intervals and p-values.

Analysis of HIT-6

The main secondary analysis of the HIT-6 Total Score will be performed using a linear mixed effects model for a normally distributed outcome. The mixed effects model will relate the mean HIT-6 scores at weeks 4, 8, 12, and 16 of treatment to a) the baseline (week 0) HIT-6 score, b) the randomized treatment group, c) the follow-up visit, defined as a categorical variable, and d) the interaction of the randomized treatment group with follow-up visit. An unstructured covariance model will be used to account for repeat observations over the three follow-up assessments. The main contrast to evaluate the treatment effect will compare the mean HIT-6 scores over the 4, 8, 12 and 16 week visits; additional exploratory contrasts will compare the HIT-6 scores at weeks 4, 8, 12, and 16 individually.

Sample Size and Power

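### The main HIT-6 contrast averages in the Week 4 score, taken before any lenses are worn, so with equal visit weights it estimates three quarters of the mean Week 8–16 lens effect.

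*Combined protocol and SAP*

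**What the plan says.** The HIT-6 paragraph (section 4, item 9, Analysis of HIT-6) states: "The mixed effects model will relate the mean HIT-6 scores at weeks 4, 8, 12, and 16 of treatment". The covariates are the week 0 score, arm, visit and arm-by-visit interaction. It then sets the estimand: "The main contrast to evaluate the treatment effect will compare the mean HIT-6 scores over the 4, 8, 12 and 16 week visits". Separate contrasts at each of the four weeks are labelled exploratory.

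The visit schedule places Week 4 before treatment. The four-week baseline period is one "during which no study lenses will be worn" (item 6, Baseline Visit 1). At Visit 2, "Subjects whose diaries meet these criteria will complete a questionnaire and receive their study spectacles". Table 1 lists HIT-6 at Week 4 alongside "Receive glasses/Check glasses fit".

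Other parts of the plan treat follow-up as starting after Week 4:
- Within the HIT-6 paragraph itself: "An unstructured covariance model will be used to account for repeat observations over the three follow-up assessments".
- Exploratory Outcomes, item b, names the three follow-up HIT-6 assessments as weeks 8, 12 and 16.
- The primary analysis covers a 12-week follow-up, "using the proportion of headache days during the 4-week baseline as a covariate".

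The Numeric outcomes paragraph repeats Week 4 as a follow-up visit.

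**The concern.** A score taken before the lenses are dispensed cannot carry a lens effect. Averaging it into the treatment contrast adds a term with expectation zero and pulls the estimate toward no difference. HIT-6 is the designated main secondary outcome, tested at two-sided 0.05 beside the primary and set apart from the analyses called exploratory. As written, its headline estimate would be diluted, and the undiluted differences at weeks 8, 12 and 16 would appear only as exploratory contrasts.

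The paragraph also supports two incompatible programs. One follows the contrast sentence and uses four visits; the other follows the covariance sentence and uses three. They give different estimates and p-values, so the choice should not remain open once unmasked results can be seen.

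**Working it through.** **Is Week 4 pre-lens?** Randomization is at week 0, with no lens wear until the Week 4 visit. Table 1 and the Visit 2 text both put the questionnaire at the dispensing visit, ahead of the glasses. Could the week labels count from dispensing instead? No: the total study duration is 16 weeks, so lens wear lasts 16 − 4 = 12 weeks and a sixteenth week of treatment does not exist.

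**Estimand.** Let d_w be the expected arm difference at week w. Randomization and no lens wear give d4 = 0. The arm-by-visit interaction makes each d_w a separate parameter. With equal visit weights:

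(d4 + d8 + d12 + d16)/4 = (0 + d8 + d12 + d16)/4 = 0.75 × (d8 + d12 + d16)/3.

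Flat (0,1,1,1), rising (0,1,2,3) and falling (0,3,2,1) patterns all give 0.75. This step needs no SD or correlation.

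A simulation of 4,000 trials with 63 per arm (70 less the plan's 10% loss), assuming SD 6, correlation 0.5 and a true lens effect of −2 points, gave mean estimates of −1.504 (four visits) and −2.002 (three visits). The ratio is 0.751, and power was 62% against 82%.

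**Power.** The plan states no HIT-6 power, SD or correlation, so there is no figure of its own to reproduce and everything here is assumption. I set the Week 8/12/16 contrast, adjusted for week 0, to 80% power (two-sided 0.05, normal approximation, complete data, constant effect). For unit variance and exchangeable correlation r:

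- variance as written: (1 + 3r)/4 − r²
- variance for weeks 8, 12, 16: (1 + 2r)/3 − r²
- noncentrality ratio k = 0.75 × √(variance for three visits / variance as written)
- power = Φ((1.960 + 0.842)k − 1.960); sample-size ratio = 1/k²

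At r = 0.55 the variances are 0.3600 and 0.3975, so k = 0.75 × √(0.3975/0.3600) = 0.788. The standard error falls by only about 5%, while the expected difference falls by 25%.

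| Assumed correlation | k | Power as written | Sample ratio |
|---|---|---|---|
| Exchangeable 0.50 | 0.791 | 60.1% | 1.60 |
| Exchangeable 0.55 | 0.788 | 59.8% | 1.61 |
| Exchangeable 0.70 | 0.782 | 59.2% | 1.63 |
| AR(1) 0.5 | 0.849 | 66.2% | 1.39 |
| AR(1) 0.9 | 0.868 | 68.1% | 1.33 |
| Declining 0.70/0.65/0.60/0.55 | 0.819 | 63.1% | 1.49 |
| Exchangeable 0.55, Week 4 SD 0.8 × the rest | 0.828 | 64.1% | 1.46 |
| Exchangeable 0.55, Week 4 SD 1.2 × the rest | 0.750 | 55.6% | 1.78 |
| Block: pre-lens 0.8, lens 0.8, between 0.5 | 0.923 | 73.5% | 1.17 |
| Block: 0.8, 0.8, between 0.3 | 0.952 | 76.0% | 1.10 |
| Block: pre-lens 0.9, lens 0.8, between 0.5 | 0.959 | 76.6% | 1.09 |

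From a 95% benchmark at exchangeable 0.55, power as written is 81.1%, a loss of 14 points.

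**Reach of the Numeric outcomes paragraph.** It covers only outcomes measured at all of those visits. In Table 1 that is HIT-6 alone; photophobia and ADL are at baseline and at Week 16 ("Final photophobia, ADL and masking questionnaires").

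**The case against.** The strongest reply concerns weight. HIT-6 is secondary, the error is conservative, the primary endpoint and type I error are untouched, no HIT-6 power was promised, and the separate Week 8, 12 and 16 contrasts would still be reported. All of that is true. It limits the harm but leaves the designated main secondary contrast estimating the wrong quantity.

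The reference to three follow-up assessments suggests a drafting slip, and perhaps nobody intends to include Week 4. That is plausible, but the sentence defining the contrast lists Week 4 explicitly, so the dilution follows if that sentence is obeyed.

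The 0.75 has conditions. Equal weights are the plain reading of a mean over visits but are not spelled out. The factor describes expected values: in the simulation the ratio of the two estimates in a single trial ran from about 0.43 to 0.92 (5th to 95th percentile). Because Visit 2 may be remote and forms may be mailed or entered in REDCap, an occasional late Week 4 form could follow dispensing. These points qualify the figure without changing the conclusion.

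The power loss is soft. Some block structures bring it down to 3.4–4.0 points, so no useful lower bound can be claimed.

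Finally, Week 4 could stay in the model without biasing the later differences, given the interaction and unstructured covariance, and might help with missing data. This stands: the contrast is what dilutes the effect.

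**Conclusion.** The concern holds. If the four-visit wording is followed, the main HIT-6 contrast has an expected value of 0.75 of the mean lens effect over weeks 8–16. This rests on equal visit weights and on Week 4 forms being completed before lens wear; it does not depend on the effect's shape over those visits or on any correlation.

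The power loss depends on correlations the documents do not give. From an 80% benchmark it is about 20 points under exchangeable correlation 0.5–0.7 (about 1.6 times the sample to recover it). It is roughly 12 to 24 points across the exchangeable, AR(1), declining and unequal-SD cases, and 3 to 7 points in the block cases. Power fell in every structure tried. The rule as written is wrong for its purpose and conflicts with the plan's own definition of follow-up, so it should be corrected before unmasking.

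**What to change.** Before unmasked data are seen, and dated accordingly:

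1. Reword the HIT-6 paragraph so that the outcomes are scores at study weeks 8, 12 and 16 (4, 8 and 12 weeks of lens wear), modelled on week 0 HIT-6, arm, visit and arm-by-visit. Define the main contrast as the equal-weight average arm difference over those three visits.
2. Remove Week 4 from the treatment outcomes and from the exploratory treatment contrasts. A Week 4 comparison may remain as a pre-lens balance check. If Week 4 is kept in the model to support the missing-data assumption, label it pre-lens and give it zero weight in every treatment contrast.
3. Align the visit list in the Numeric outcomes paragraph.

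The cost is SAP wording only. HIT-6 is already collected at weeks 0, 4, 8, 12 and 16, so no visit, instrument or subject is added.

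A separate, optional refinement is to use the Week 4 score as a second pre-lens covariate. Under the same assumptions, 80% power becomes about 89% at exchangeable 0.55 and 84–93% under AR(1) 0.5–0.9, but only 81.8% in the 0.8/0.8/0.5 block case. The correction does not depend on it.
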